5.1.1.2.1 Safety

Safety endpoints will be analyzed descriptively for subjects in safety analysis set (SafAS). Solicited reactions (solicited injection site and systemic reactions), unsolicited AEs, SAEs, and AESIs will be summarized. The main parameters will be described by single proportions with the 95% CI (Clopper-Pearson method) (9).

- Occurrence, nature (Medical Dictionary for Regulatory Activities [MedDRA] PT), duration, intensity, and relationship to vaccination of any unsolicited systemic AEs reported in the 30 minutes after each vaccination.
- Occurrence, time to onset, number of days of occurrence, intensity, action taken, and whether the reaction led to early termination from the study, of solicited (prelisted in the subject's diary card and CRB) injection site reactions and systemic reactions occurring up to 7 days after each vaccination.
- Occurrence, nature (MedDRA system organ class [SOC] and PT), time to onset, duration, intensity, relationship to vaccination (for systemic AEs only), and whether the event led to early termination from the study, of unsolicited AEs up to 28 days after each vaccination.
- Occurrence, nature (MedDRA SOC and PT), time to onset, seriousness criteria, relationship to vaccination, outcome, and whether the event led to early termination from the study, of SAEs (including AESIs) throughout the study.
- Occurrence, nature (MedDRA PT), time to onset, and relationship to vaccination of AESIs throughout the study.

5.1.1.2.2 Immunogenicity

Immunogenicity endpoints, which are described in [Section 4.4.2.1](#), will be summarized with 95% CIs. The 95% CIs for the geometric mean titers (GMTs) and the geometric means of titer ratios (GMTRs) will be calculated using normal approximation of log-transformed titers. The 95% CIs for the single proportions will be based on the Clopper-Pearson method. When age stratification is not considered, the ratios of GMTs (GMT ratios) will be obtained between groups with the 95% CIs calculated using normal approximation of log-transformed titers. The differences in the seroconversion rates between groups will be computed along with the 2-sided 95% CIs by the Wilson-Score method without continuity correction (10). Additional parameters may be displayed as appropriate.

Reverse cumulative distribution curves against each strain will be performed for baseline (V01) and post-vaccination immunogenicity (D28 or D56 as appropriate).

The immunogenicity analysis set (IAS) will be used for the main immunogenicity analyses.

The details about the calculations of the 95% CI for the GMT ratio between 2 groups are as following:

Logarithmic transformation of the individual titers will be calculated first. Assuming that individual \log_{10} (titer) is normally distributed, the 95% CI for the difference in \log_{10} (GMT) between group i and group j will be in the form:

$$\bar{X}_i - \bar{X}_j \pm t(1-\alpha/2, n_i + n_j - 2) \cdot S \sqrt{1/n_i + 1/n_j}$$

where $\bar{X}_i = \log_{10}(\text{GMT})$ is the mean of $\log_{10}(\text{titer})$ of Group i ,

$S^2 = [(n_i - 1) S_i^2 + (n_j - 1) S_j^2] / (n_i + n_j - 2)$ is the pooled sample variance,

n_i and S_i^2 are the sample size and sample variance of Group i ,

$t(1-\alpha/2, n_i + n_j - 2)$ is the $100(1-\alpha/2)$ percentile of the t -distribution with degrees of freedom (df) = $n_i + n_j - 2$.

The 2-sided 95% CI of the difference in proportions will be computed using the Wilson Score method without continuity correction, quoted by Newcombe (10) as follows:

Let $\hat{\theta} = \pi_A - \pi_B$, then $L = \hat{\theta} - \delta$ and $U = \hat{\theta} + \varepsilon$ are respectively the lower and the upper limits of the CI, where:

$$\delta = Z_{0.025} \sqrt{\left\{ \frac{l_1(1-l_1)}{n_1} + \frac{u_2(1-u_2)}{n_2} \right\}}$$

$$\varepsilon = Z_{0.025} \sqrt{\left\{ \frac{l_2(1-l_2)}{n_2} + \frac{u_1(1-u_1)}{n_1} \right\}}$$

l_1 and u_1 are calculated from the CI of the single proportion in Group A given by:

$$\frac{(2n_1 p_A + Z_{0.025}^2 \pm Z_{0.025} \sqrt{(Z_{0.025}^2 + 4n_1 p_A(1-p_A))})}{2(n_1 + Z_{0.025}^2)}$$

l_2 and u_2 are calculated from the CI of the single proportion in Group B given by:

$$\frac{(2n_2 p_B + Z_{0.025}^2 \pm Z_{0.025} \sqrt{(Z_{0.025}^2 + 4n_2 p_B(1-p_B))})}{2(n_2 + Z_{0.025}^2)}$$

where $Z_{0.025}$ is the upper 97.5th percentile of the standard normal distribution.

When age stratification is considered, the age-stratified GMT ratio between each QIV-HD group (30 μ g, 45 μ g, and 60 μ g) and the pooled QIV-SD group will be reported. The corresponding 95% CIs of GMT ratios will be calculated using an analysis of variance (ANOVA) model of \log_{10} -transformed titers considering vaccine group as the main effect and age group as a covariate.

The 95% CI of the difference in seroconversion rates between each QIV-HD group (30 μ g, 45 μ g, and 60 μ g) and the pooled QIV-SD group will also be stratified on age effect and calculated using the Wald method (normal approximation). Weighted average of the difference over strata will be calculated using the Minimal Risk weights method (11). The details are as follows.

The 100(1- α)% two-sided CI for the difference in proportions between two groups A and B using the Minimum Risk Weights will be in the form:

$$\hat{\delta}_w \pm Z_{\alpha/2} \sqrt{\left\{ \sum_{i=1}^s w_i^2 \hat{V}(\hat{\delta}_i) \right\}}$$

Where $\hat{\delta}_w = \sum_{i=1}^s w_i \delta_i$ is the estimated weighted average of the proportion difference over strata; $\delta_i = \hat{p}_{iA} - \hat{p}_{iB}$ is the estimated proportion difference between group A and B at stratum i ($i=1, \dots, s$);

$\hat{V}(\hat{\delta}_i) = \frac{\hat{p}_{iA}(1-\hat{p}_{iA})}{n_{iA}} + \frac{\hat{p}_{iB}(1-\hat{p}_{iB})}{n_{iB}}$ is the estimated variance of proportion difference between group A and B at stratum i , where n_{iA} and n_{iB} are the sample sizes of group A and B at stratum i ;

$Z_{\alpha/2}$ is the $100(1 - \alpha/2)$ th percentile of the standard normal distribution;

w_i is the weight assigned at stratum i , where $\sum_{i=1}^s w_i = 1$.

The Minimum Risk method computes the weights w_i as follows:

$$w_i = \frac{\beta_i}{\sum_{k=1}^s V_k^{-1}} - \left(\frac{\alpha_i V_i^{-1}}{\sum_{k=1}^s V_k^{-1} + \sum_{k=1}^s \alpha_k \delta_k V_k^{-1}} \right) \left(\frac{\sum_{k=1}^s \delta_k \beta_k}{\sum_{k=1}^s V_k^{-1}} \right)$$

where $\alpha_i = \delta_i \sum_{k=1}^s V_k^{-1} - \sum_{k=1}^s \delta_k V_k^{-1}$, $\beta_i = V_i^{-1} \left(1 + \alpha_i \sum_{k=1}^s f_k \delta_k \right)$, $V_i = V(\hat{\delta}_i)$, and f_i is the fraction of subjects in the target population that belong in stratum i ($\sum_{i=1}^s f_i = 1$).

In addition, a sensitivity analysis will be performed with adjustment on the baseline titers. When comparing the GMT ratio between each QIV-HD group (30 μ g, 45 μ g, and 60 μ g) and the pooled QIV-SD group, the 95% CI will be stratified on both age effect and baseline titers and calculated using General Linear Model (GLM). When comparing the GMT ratio between each QIV-HD group and the QIV-SD group per age group, an ANCOVA model will be used when considering the baseline titer as a covariate. Results will be presented in Appendix 15 of the CSR.

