Site staff will connect to the IRT, enter the identification and security information, and confirm a minimal amount of data in response to IRT prompts. The IRT will then provide the group assignment and have the site staff confirm it. Stratified randomization will be applied for all

subjects enrolled in each group stratified by previous influenza vaccination status and country. Site will not be a strata for randomization due to the small sample size in each group. The allocation ratios between investigational HD vaccines to the comparators are: 3:1 ratio in groups 1, 2, 3, 5, 9, and 10; 3:3:1 ratio in group 12; and 1:1 ratio in groups 4, 6, 7, 8, 11, and 13. The full detailed procedures for group allocation are described in the Operating Guidelines. If the subject is not eligible to participate in the study, then the information will only be recorded on the subject recruitment log.

Subject numbers that are assigned by the IRT will consist of a 12-digit string (a 3-digit country identifier [840 for the US and 124 for Canada], a 4-digit study site identifier, and a 5-digit subject identifier). For example, Subject 840000100005 is the fifth subject enrolled in Center Number 1 in the US.

Subject numbers should not be reassigned for any reason.

Dose numbers will be 7 digits long. Dose numbers are not used for packaging but only in the IRT system.

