5.1.1.2 Statistical Methods

For the cohorts controlled by the non-adjuvanted QIV-SD, results will be described per stage, according to vaccine received, per age group. Age groups will also be pooled within the same vaccine group for the main endpoints. When age groups are pooled, since age distributions between QIV-HD groups and the pooled QIV-SD group are different, the Simpson Paradox might exist. Therefore, each QIV-HD group (30 μ g, 45 μ g, and 60 μ g) will be compared with its corresponding and restricted QIV-SD group (ie, QIV-SD control group restricted to relevant study groups for comparison to QIV-HD at 30 μ g, QIV-HD at 45 μ g, and QIV-HD at 60 μ g respectively) to reduce the potential bias. If any of the stages are not completed, analyses for the higher dose or next stage will not be performed.

For the cohort controlled by the adjuvanted TIV, results will be described according to vaccine received.

For main safety analyses, results will be described based on both “after any vaccination” and “after each vaccination”.

For main immunogenicity analyses, results will be described based on both “after last vaccination” and “after each vaccination”. Subgroup immunogenicity analyses per previous vaccination status and/or baseline serostatus may be presented when appropriate. Comparison between each QIV-HD group (30 μ g, 45 μ g, and 60 μ g) and the pooled QIV-SD group will also be performed stratified on age groups for immunogenicity endpoints.

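### The restricted QIV-SD comparison is left with an unadjusted interval that is wider than needed, and with an age-confounded ratio if Stage 4 does not use 60 µg

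*SAP*

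**What the plan says.** SAP 5.1.1.2 raises Simpson's paradox for pooled age groups. As its remedy, each QIV-HD dosage "will be compared with its corresponding and restricted QIV-SD group", meaning QIV-SD recipients from the study groups in which that dosage was given. The same section adds a second comparison: each dosage against "the pooled QIV-SD group will also be performed stratified on age groups for immunogenicity endpoints".

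SAP 5.1.1.2.2 then gives the methods.

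- **Unstratified GMT ratio:** "When age stratification is not considered, the ratios of GMTs (GMT ratios) will be obtained between groups", with a t interval on log10 titre in which S² "is the pooled sample variance" of the two arms. There are no covariates.
- **Unstratified seroconversion:** "The differences in the seroconversion rates between groups will be computed along with the 2-sided 95% CIs by the Wilson-Score method", without strata.
- **Age-stratified:** an ANOVA "considering vaccine group as the main effect and age group as a covariate", and minimum-risk weights for seroconversion. Both are written for the pooled QIV-SD group.
- **Baseline titre:** "a sensitivity analysis will be performed with adjustment on the baseline titers". It covers the comparison with pooled QIV-SD, and comparisons within one age group.

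Protocol 6.5 fixes the allocation ratio in each study group and randomises "subjects enrolled in each group stratified by previous influenza vaccination status and country". Prior vaccination enters no between-group model; SAP 5.1.1.2 mentions it only as an optional subgroup.

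**The concern.** Every adjusted method is tied to some other comparison, so the restricted one inherits the plain two-sample interval. That interval treats the two arms as simple samples from one mixed-age population. The design did more than that: it fixed the vaccine ratio within each study group and prior-vaccination stratum. Variation between those cells therefore drops out of the treatment contrast, yet it is still counted in S.

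Protocol 1.4 says the study is meant to select the dosage for Phase III. With no hypothesis tests, the estimates and their intervals are the whole result. The 30 and 45 µg restricted comparisons have only 40 controls each, so avoidable width matters most there.

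**Working it through.** **Sizes (Protocol Table 5.1; SAP 5.5).** The total is 6×40 + 90 + 60 + 2×60 + 2×60 + 70 = 700, as stated. Restricted comparisons:

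- 30 µg (groups 1, 3, 9, 12): 120 vs 40, four age groups, 30 vs 10 in each.
- 45 µg (groups 2, 5, 10, 12): 120 vs 40, likewise.
- 60 µg (groups 4, 11, 13): 105 vs 105; or 165 vs 165 if groups 6 and 7 receive 60 µg.

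In these configurations the ratio is constant over study groups (3:1 or 1:1), so the crude contrast is not confounded by age.

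**Width of the GMT-ratio interval.** The log10 half-width is t × SD × √(1/n1 + 1/n2). The documents give no SD, age means or correlations. I assume mean log10 titres of 1.6, 1.9, 2.2 and 2.4 from youngest to oldest, within-age SD 0.5, and a within-age correlation of 0.5 with D0 titre.

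For 30 µg, √(1/120 + 1/40) = 0.1826 and t ≈ 1.975. The mean over ages is 2.025. The between-age variance is (0.425² + 0.125² + 0.175² + 0.375²)/4 = 0.0919.

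- As planned: SD = √(0.25 + 0.0919) = 0.585; half-width 0.211; interval is the estimate ×/÷ 1.62.
- Stratified: SD = 0.5; half-width 0.180; ×/÷ 1.51. The planned interval is 17% wider.
- Stratified plus D0: SD = 0.5 × √0.75 = 0.433; half-width 0.156; ×/÷ 1.43. The planned interval is 35% wider.

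The planned interval spans 1.975 × 0.585/0.5 ≈ 2.31 true standard errors each side, which is about 97.9% coverage; a simulation agrees. For 60 µg at 165 vs 165, the same means give ×/÷ 1.34 planned and ×/÷ 1.28 stratified, again 17%.

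**Sensitivity.** A separate simulation of the 120 vs 40 design included study-group, prior-vaccination and D0 effects. Mean log10 half-widths were:

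| Covariate effect | Unadjusted | Group + stratum | Plus D0 | Excess | Unadjusted coverage |
|---|---|---|---|---|---|
| None | 0.180 | 0.180 | 0.180 | 0%, 0% | 94.5% |
| Moderate (R² ≈ 0.17) | 0.175 | 0.169 | 0.163 | 4%, 7% | 95.9% |
| Strong (R² ≈ 0.44) | 0.189 | 0.165 | 0.145 | 15%, 30% | 97.5% |

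The first row shows that adjustment costs essentially nothing when it is not needed.

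**Seroconversion (120 vs 40, QIV-HD 10 points above control).** With all control rates at 50%, the Wald half-width is 1.96 × √(0.6×0.4/120 + 0.5×0.5/40) = 17.8 points, and stratifying by study group leaves it at 17.8. With control rates of 35, 45, 60 and 70% it falls from 17.7 to 17.1 (ratio 0.96). With 20, 40, 60 and 80% it falls from 17.8 to 15.9 (ratio 0.89). The gain is 0–11%.

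**If Stage 4 does not use 60 µg.** Table 5.1 allows 30, 45 or 60 µg in groups 6 and 7, both 6 to < 36 months and both 1:1. At 45 µg, assuming groups 6 and 7 count as relevant study groups, the restricted comparison becomes 180 vs 100. The share under 36 months is 90/180 = 50% against 70/100 = 70%. Under the assumed means:

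- QIV-HD: 0.5×1.6 + (1.9 + 2.2 + 2.4)/6 = 1.883
- QIV-SD: 0.7×1.6 + 0.1×(1.9 + 2.2 + 2.4) = 1.770

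The difference is 0.113, a crude GMT ratio of about 1.30 with no vaccine effect. Stage 4 at 30 µg gives the same counts for that dosage.

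**The case against.** The strongest objection is that the SAP already plans a tighter estimate per dosage. The age-stratified comparison uses all 235 QIV-SD controls. For 30 µg, with 30 per age group against 80, 65, 50 and 40 controls, the weights 1/(1/30 + 1/n) sum to 78.2. The half-width is 1.967 × 0.5/√78.2 = 0.111, or ×/÷ 1.29, and ×/÷ 1.25 with D0. Both are narrower than anything adjustment can give the restricted comparison (×/÷ 1.51 and 1.43). This stands. Much of the restricted width comes from having only 40 controls (standard-error factor 0.183, against 0.112 with all 235), which no model removes. A reader might infer that the plan lacks a precise pooled estimate, or that the restricted comparison must become the headline. The documents support neither. They name no headline, and the restricted comparison is there to reduce bias.

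The link to the plain interval is an inference. No sentence assigns it, and the detailed outputs are deferred to the full tables, listings and figures. That is itself a reason to add a sentence.

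A reader might also infer that the intervals always over-cover or are invalid. They do not over-cover when covariates have no effect, and in the moderate case coverage is 95.9%. When Stage 4 uses 60 µg, any error is on the conservative side, in an unpowered descriptive study. Nor is D0 titre ignored throughout: fold-rise and seroconversion are defined relative to it (SAP 4.4.2.2 and 4.4.2.3). The gap concerns the post-vaccination GMT ratio.

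**Conclusion.** The concern holds as a loss of precision in the restricted GMT-ratio comparison. The direction follows from the design; the size does not, because the documents give no SDs, age differences or correlations with D0 titre. The excess width is zero with no covariate effect. Under the values tried above it is about 4–17% against stratification and about 7–35% with D0 added. The SAP's own worry about Simpson's paradox implies that it expects age to matter, so zero is the less likely end. The seroconversion gain is small, 0–11%.

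Validity is affected only if Stage 4 uses 30 or 45 µg. The vaccine ratio then differs between study groups, and the crude restricted ratio reintroduces the age confounding it was meant to reduce. The figure of about 1.30 rests entirely on the assumed age means.

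**What to change.** In SAP 5.1.1.2.2, state the method for the restricted comparison:

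- **GMT ratio:** a linear model of log10 titre on vaccine, study group and prior-vaccination stratum, with a second version adding log10 D0 titre. Keep the unadjusted ratio as supportive.
- **Seroconversion:** apply the stratified approach the SAP already describes, by study group, to the restricted comparison. With about 10 controls in many study groups the normal approximation is rough, so report the planned unstratified Wilson-score interval alongside.

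Which pooled comparison leads the report need not change.

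The cost is SAP wording and programming; the strata and D0 titres are already collected. One drawback: Protocol 5.1.4 still vaccinates a child whose V01 blood draw fails, such a child can be in the IAS, and SAP 5.3.2 does not impute. These children drop out of the D0-adjusted version, which is why the stratified model without D0 is kept. The number excluded should be reported.

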#### *Vaccination*

All eligible subjects will be randomized to receive 1 or 2 doses of either QIV-HD, Fluarix® Quadrivalent (unadjuvanted QIV-SD), or FLUAD Pediatric® (adjuvanted TIV). The dosage of QIV-HD that is administered will depend on both the age of the subject and the stage at which he / she is enrolled.

- Subjects 9 to 17 years of age will receive 1 dose of the QIV-HD or the comparator vaccine on D0.
- Previously influenza vaccinated subjects 6 months to 8 years of age will receive 1 dose of the QIV-HD or the comparator vaccine on D0.
- Previously influenza unvaccinated subjects 6 months to 8 years of age will receive 2 doses of the QIV-HD or the comparator vaccine. Each dose will be administered 28 days apart (at D0 and D28).

Of note, the highest dosage with an acceptable safety review in prior stages will determine the dose evaluated in Stage 4.

An unblinded administrator at each site will administer the vaccine.

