#### **5.1.4 Visit Procedures**

##### ***Visit 1 (Day 0): Inclusion, Randomization, Blood sample, and Vaccination – for all subjects***

###### **The Investigator or delegate will:**

- 1) Give the subject and / or subject's parent / guardian information about the study.
- 2) Obtain informed consent and assent (for subjects 7 to 17 years of age) and answer any questions to ensure that the subjects and/or subject's parent / guardian have been informed of all aspects of the study that are relevant to their decision to participate.
- 3) Date and sign the ICF (and assent form for subjects 7 to 17 years of age) after it has been signed and dated by the subject or subject's parent / guardian. Retain the original and give a signed copy to the subject or subject's parent / guardian.
- 4) Check all inclusion and exclusion criteria (see [Section 5.2.4](#) and [Section 5.2.5](#), respectively) through physical examination and medical interview of the subject and / or subject's parent / guardian. If the subject is not eligible, only the specific form entitled "Recruitment log" will state the subject identification, no CRB will be completed.
- 5) Collect relevant demographic information (eg, date of birth, sex, ethnicity, and race).
- 6) For females of childbearing potential, conduct a urine pregnancy test.
- 7) Obtain verbal information on medical history.
- 8) Obtain information on seasonal influenza vaccination and any influenza diagnosis as follows:
  - For previously influenza unvaccinated subjects, confirm that the subject has not been vaccinated with any seasonal influenza vaccine since birth and has never had a known influenza diagnosis.

Note: For the US sites, in following the Advisory Committee on Immunization Practices (ACIP) Guidelines, this study will consider subjects 6 months to 8 years of age who have never been vaccinated against influenza or who have not received at least 2 doses of seasonal influenza vaccine in a prior influenza season as "previously influenza unvaccinated subjects" when enrolling and thus these subjects will receive 2 doses of study vaccine at least 28 days apart. Subjects whose vaccination history is unknown will

also be considered as “previously influenza unvaccinated subjects” when enrolling and also receive 2 doses of study vaccine at least 28 days apart.

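### The age-adjusted GMT ratios against pooled QIV-SD omit previous vaccination status, a randomisation stratum that sets one or two doses below 9 years, so status mix can bias them

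*SAP*

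**What the plan says.** SAP 5.1.1.2.2 obtains the age-stratified GMT ratio of each QIV-HD dosage to pooled QIV-SD from an ANOVA "considering vaccine group as the main effect and age group as a covariate". In the sensitivity analysis against the same pooled control, "the 95% CI will be stratified on both age effect and baseline titers", using a general linear model. The last of the three models is by age: "When comparing the GMT ratio between each QIV-HD group and the QIV-SD group per age group, an ANCOVA model will be used", with baseline titre as covariate. None of the three contains previous vaccination status.

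That status is built into the design. Protocol 6.5 randomises all "subjects enrolled in each group stratified by previous influenza vaccination status and country". Protocol 5.1.3 states: "Previously influenza unvaccinated subjects 6 months to 8 years of age will receive 2 doses of the QIV-HD or the comparator vaccine". Previously vaccinated children of that age, and everyone aged 9 to 17, receive one dose. For US sites, Protocol 5.1.4 explains who counts as unvaccinated: "this study will consider subjects 6 months to 8 years of age who have never been vaccinated against influenza", together with children short of two prior doses or of unknown history.

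SAP 5.1.1.2 states: "For main immunogenicity analyses, results will be described based on both" the last and each vaccination. It warns of Simpson's paradox from pooling ages and therefore says that each QIV-HD dosage "will be compared with its corresponding and restricted QIV-SD group". Status enters only through subgroup analyses that are optional.

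**The concern.** Stratified randomisation protects a comparison made within study groups. Pooled QIV-SD is assembled across groups and stages, so status can differ between a QIV-HD dosage and its pooled control inside the same age group, and an age term cannot remove that. The clearest case is 6 to <36 months, where 60 of the 80 controls come from Groups 6 and 7, fixed at 30 unvaccinated and 30 vaccinated. If Stage 4 uses 60 µg, the 30 and 45 µg recipients of that age come only from Groups 3 and 5, for which SAP 5.5 sets no status quota.

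Below 9 years, status also decides whether the result after the last vaccination is a D28 titre after one dose or a D56 titre after two. The study is meant to select a Phase III dosage, so a distortion that differs by dosage matters for interpretation. The SAP already reasons this way about age; status has the same structure.

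**Working it through.** **Inputs from the documents** (Protocol Table 5.1; SAP 5.5). Group sizes sum to 6×40 + 90 + 60 + 2×60 + 2×60 + 70 = 700, the stated total. With Stage 4 at 60 µg (an assumption; Protocol 12.1.1.2 mentions a pooled 60 µg group over the two countries), the planned US numbers are:

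| Age | 30 µg | 45 µg | 60 µg | QIV-SD |
|---|---|---|---|---|
| 6 to <36 months | 30 | 30 | 60 | 80 |
| 36 months to <5 years | 30 | 30 | 45 | 65 |
| 5 to 8 years | 30 | 30 | 30 | 50 |
| 9 to 17 years | 30 | 30 | 30 | 40 |
| Total | 120 | 120 | 165 | 235 |

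**Assumptions.** The unvaccinated share in the mixed groups and the log10 titre gap by status (0.3 to 0.5) are not in the documents. Ratios below take unvaccinated children as the higher group; if they are the lower, take reciprocals. There is no true vaccine effect, and the gap is zero at 9 to 17 years.

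**Formula, one dosage against QIV-SD.** Bias (log10) = gap × Σ wₖdₖ / Σ wₖ over age groups. Here dₖ is the unvaccinated share in QIV-HD minus that in QIV-SD, and wₖ = n(HD)·n(SD)/[n(HD)+n(SD)]. At 30 µg the weights are 21.82, 20.53, 18.75 and 17.14, sum 78.24.

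**Constant 20% mix.** Only 6 to <36 months is unbalanced. The QIV-SD share is (30 + 0.2×20)/80 = 0.425, so d = 0.20 − 0.425 = −0.225.
- Gap 0.3: −0.225 × 0.3 × 21.82/78.24 = −0.0188, a ratio of 0.958.
- Gap 0.5: −0.225 × 0.5 × 21.82/78.24 = −0.0314, a ratio of 0.930.

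**Mix of 40, 50, 60% in Stages 1, 2, 3, at 30 µg.** From youngest to oldest below 9 years:
- d = 0.50 − 41/80 = −0.0125
- d = 0.40 − 36/65 = −0.154
- d = 0.40 − 27/50 = −0.14

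The weighted mean is −0.0774, giving 0.948 (gap 0.3) and 0.915 (gap 0.5).

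**Joint fit** of all dosages by weighted least squares on the planned cells (log10 titre on vaccine and age group), ratios at 30 / 45 / 60 µg:

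| Unvaccinated share | Gap 0.3 | Gap 0.5 |
|---|---|---|
| 50% throughout | 1.000 / 1.000 / 1.000 | 1.000 / 1.000 / 1.000 |
| 40% throughout | 0.986 / 0.986 / 1.007 | 0.977 / 0.977 / 1.011 |
| 20% throughout | 0.958 / 0.958 / 1.020 | 0.932 / 0.932 / 1.033 |
| 40, 50, 60% by stage | 0.949 / 0.999 / 1.013 | 0.916 / 0.998 / 1.021 |

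Shares of 60% and 80% give the reciprocals of 40% and 20%. At a constant 20%, the apparent 60-versus-30 µg contrast is 1.020/0.958 = 1.06 to 1.033/0.932 = 1.11.

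**With status added by age group**, every ratio in the table is 1.000. The SE at 30 and 45 µg goes from 0.1127 to at most 0.1130 SD units, or 0.1158 at 30 µg if the mix is 20, 50, 80%.

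**Restricted own-group comparison.** At 30 µg (Groups 1, 3, 9, 12) and at 45 µg (Groups 2, 5, 10, 12) every group has three QIV-HD recipients per control. At 60 µg (Groups 4, 6, 7, 11, 13) the ratio is 1:1. Age, status and stage are therefore balanced, and the ratio is 1.000. At 30 and 45 µg the SE is √(1/120 + 1/40) = 0.183 SD units.

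**Concurrency.** Same-age, same-stage controls at 30 µg number 10 + 10 + 10 + 40 = 70 (Groups 1, 3, 9, and 12 with 13). At 45 µg they also number 70 (Groups 2, 5, 10, and 12 with 13). The other 165 of 235 (70%) are from a different stage. An assumed drift of 0.05 log10 per stage gives 0.874, 0.952 and 1.044 at 30, 45 and 60 µg, essentially unchanged when status is added.

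**The case against.** The strongest reply is that the SAP already requires a comparison free of this problem: the restricted own-group ratio, balanced on status and stage without a model. That stands. But the pooled ratio will also be reported, it is the more precise one at 30 and 45 µg (SE 0.113 against 0.183 SD units), and the restricted ratio does not correct it.

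The bias is also modest and rests on assumed inputs. At an assumed SD of 0.5 log10 the pooled SE is 0.5 × 0.1127 = 0.056. The 1.04- to 1.07-fold bias is then about 0.3 to 0.5 SE, against a 95% half-width of about 1.29-fold. Stage drift could be larger, and status adjustment leaves it in place. Both points stand, and the fix must say so.

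Four stronger readings are tempting but not supported:
- **That imbalance always moves 30 and 60 µg in opposite directions.** It does in the unbalanced mixes tabulated. With 80, 50, 80% over Stages 1 to 3 and a 0.5 gap, both move the same way (0.978 and 0.990, or the reciprocals).
- **That the vaccinated share must fall through the season.** Exclusion 4 removes recently vaccinated children of one status, but exclusion 5 also removes children of the other status who have been vaccinated. No trend by stage is documented.
- **That the ratio at 6 to <36 months is off by 1.17- to 1.30-fold.** This is 0.225 × 0.3 to 0.5 log10 at a 20% mix. It requires all 80 QIV-SD subjects as the per-age control, before baseline adjustment. The SAP does not clearly say this, and it also reports by stage.
- **That one versus two doses affects every result.** At D28 after the first vaccination everyone has had one dose, so this part of the concern applies to the result after the last vaccination.

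**Conclusion.** The omission is real, and within-group stratification does not make it harmless for a control pooled across groups and stages. Its size depends on a mix and a gap that the documents do not give: from nil at a constant 50% mix to 1.04- to 1.07-fold at 20% or 80% for 30 and 45 µg, and more at 30 µg if the mix shifts by stage. The direction is unknown. In some mixes the error could mimic or hide a dose response; in others it could not. What remains after the planned baseline adjustment has not been calculated: baseline titre may partly stand in for status, but it does not encode the number of doses. No hypothesis is tested, so no error rate is affected. This is an inexpensive improvement to a secondary descriptive comparison, not a flaw that undermines the study.

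**What to change.** In SAP 5.1.1.2.2, add previous vaccination status, as randomised, to the pooled GMT-ratio ANOVA and to the baseline-adjusted GLM. Code it as one previously-unvaccinated indicator in each of the three age groups below 9 years, and none at 9 to 17 years. Put the same indicator in the per-age ANCOVA below 9 years.

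Add to the SAP that the pooled ratios at 30 and 45 µg rest mostly on non-concurrent controls (165 of 235 if Stage 4 uses 60 µg), that status adjustment does not remove stage drift, and that these ratios are to be read beside the restricted own-group ratios.

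The cost is wording and three model terms on a variable already collected for randomisation. The SE moves from 0.1127 to about 0.113 SD units, or 0.116 at 30 µg with a very uneven mix. A single status term would be simpler, but if the gap differs by age (assumed 0.1, 0.3, 0.5 log10 from oldest to youngest below 9 years, 20% mix) it leaves 0.979 at 30 and 45 µg. The age-stratified seroconversion difference uses the same pooled control and would stay unadjusted, because age-by-status strata become thin (0.2 × 30 = 6 unvaccinated QIV-HD subjects in Group 3 at a 20% mix); the SAP should note this.
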